#### **4.1.3 Rationale for DNA Mosaic-Tre env as a universal helper immunogen**

[figure not shown]
It is known that considerable T-cell help is required for the amount of affinity maturation needed to drive bnAbs and that those individuals chronically infected with HIV who spontaneously make bnAbs have higher levels of blood CD4 T cells that are phenotypically similar to T follicular helper T cells (Tfh) [25]. Previous work in non-human primates suggested that including a DNA vaccine with the protein can increase the quantity and quality of the induced antibody response compared to immunization with protein alone [26,27]. Furthermore co-administration of DNA and protein in the same limb elicited higher systemic binding and neutralizing antibodies compared to DNA alone or DNA prime followed by an antibody boost [26]. Pavlakis and colleagues illustrated the potential immunologic advantages of co-administration of protein with DNA in non-human primate studies whereby the animals that received DNA vaccine (either alone or co-administered with a protein) had higher levels of vaccine-induced T-cell responses. Moreover, the group that received DNA concurrently with protein had higher binding Ab responses than DNA or protein alone [28,29]. Pissani, et al. also showed in rabbits that DNA and protein co-administration increased the magnitude, avidity, and neutralizing potency compared to administration of protein alone. In addition, their study indicated that antibody responses using a mismatched DNA and protein elicited comparable or higher responses compared to matched vaccines [27]. These data support inclusion of a DNA vaccine in the regimen to assess and compare binding antibody responses and differential binding induced by immunization with and without the DNA. We hypothesize that the combined administration of DNA and protein will elicit stronger humoral and cellular responses than the protein alone.

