#### 4.5.1 Dose (amount and number) and schedule

Part A, the dose-finding portion of the study, will involve 5 immunizations IM with the CH505TF gp120 at 0, 2, 4, 8, and 12 months. The doses of the protein will be 20 mcg (group 1), 100 mcg (group 2), and 400 mcg (group 3). GLA-SE will be admixed with all proteins and the total dose of GLA-SE will be 10 mcg at all timepoints. The total volume for protein plus adjuvant for injection will be 1 mL, mixed 1:1 by volume.

Part B will include an additive and a sequential approach to EnvSeq-1 protein administration, both with and without the DNA Mosaic-Tre *env* vaccine. The additive approach administers CH505TF, followed by CH505TF and w53 at month 2, CH505TF + w53 + w78 at month 4, CH505w53 + w78 + w100 at month 8, CH505w78 + w100 at month 12, and CH505w100 at month 16 as follows:

Month 0	Month 2	Month 4	Month 8	Month 12	Month 16
TF	TF	TF			
	w53	w53	w53		
		w78	w78	w78	
			w100	w100	w100

This additive immunization strategy mimics natural infection with proteins being administered in the order that they evolved naturally along with some overlap with preceding mutant Envs. This strategy also ensures that each protein is administered 3 times, which may be needed for optimal immune response to each immunogen to drive the desired B cell maturation.

The sequential approach will start with the CH505TF, then administer CH505w53 at month 2, CH505w78 at month 4, and CH505w100 at months 8, 12, and 16. The sequential approach also administers the Env mutants in the order that they evolved naturally, but does not include overlapping protein vaccinations. If the sequential approach is as effective as the additive approach, the simplified immunization schedule would be preferable. The immunization schedule is attempting to compress the process of recreating the evolution of antibody responses to the CD4 binding site in a much shorter timeframe than the 2 years it took for them to develop in natural infection. Data from NHP studies support the approach. This is the first clinical study evaluating this approach in humans. As mentioned above, the dose of the proteins will be determined by the safety and immunogenicity following the third immunization in Part A.

In Part B, the vaccines will be administered at months 0, 2, 4, 8, 12, and 16 and 10 mcg of GLA-SE adjuvant will be admixed with all proteins at all timepoints. In addition, some groups will also receive co-administration of 4 mg of DNA Mosaic-Tre *env* [17] to

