### 6.1.2 Sample size calculations for immunogenicity

To address the humoral immunogenicity endpoints, the analysis will compare the area under the magnitude-breadth curve of the IgG Env binding Ab response, and will compare the frequency of memory B cells that bound to gp120CH505 TF but not to gp120CH505 TF  $\Delta$ 371, 2 weeks after the third (Part A) or fourth and sixth (Part B) vaccinations with CH505TF gp120. To estimate power, binding magnitude-breadth data were simulated assuming that the proportion of non-zero responses was 0.94 in both comparison groups. This is based on pilot data for the IgG binding Ab response in HVTN 088. For these calculations, non-zero responses, modeled on the  $\log_{10}$  scale, were drawn from a normal distribution. The mean non-zero response in group 1 was set to 4.06. This was the mean non-zero response in the HVTN 088 vaccine arm T2 (the treatment arm for vaccine naïve participants). The standard deviation (SD) of the non-zero response was set to 0.391 for both groups; this was the SD of the non-zero response in the HVTN 088 vaccine arm.

The differential binding rate is the fraction of class memory B cells that have the property of binding the two protein hooks in a differential manner (defined by flow gating). In the assay, two measurements are made simultaneously: binding to the transmitted founder CH505 virus, and binding to the  $\text{I}\Delta 371$  variant. Each of these yields a measurement of the proportion of memory B cells that bind to a target virus. While the primary interest is in the differential binding to these two viruses, which is the difference of these proportions, we will also evaluate each measure separately to further describe and explore the relationship between these measures under the scenarios represented by the arms of this trial.

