binding Ab response to a panel of gp120 proteins and of the neutralization of tier 1 and tier 2 panels of HIV-1 viruses. Each analysis will be conducted separately for each of 2 pooled comparisons (additive vs sequential, pooling over groups with and without mosaic DNA: Groups 5 and 6 combined vs Groups 7 and 8 combined; effect of mosaic DNA, pooling over groups receiving additive and sequential proteins: Groups 5 and 7 combined vs Groups 6 and 8 combined), and for each of 6 pairwise comparisons among these groups using a two- sided Wilcoxon rank sum test with 5% type-I error rate per pooled comparison and a 5%/6 type-I error rate per pairwise comparison. The sample size of 20 vaccinees per group will give 80% power to detect a true difference of 1.63 standard deviations (SDs) between the mean non-zero responses and 90% power to detect a true difference of 1.81 SDs for the pairwise comparisons. Using the mean and SD values from the HVTN 088 trial, the difference of 1.63 SDs translates to a difference of 0.637 units of  $\log_{10}$  binding magnitude; if 1 of the comparison groups has the same mean as was seen among non-negative values among vaccine recipients in the HVTN 088 trial (4.06 units), then after incorporating the expected 6% zero-valued (negative responder) measures, this corresponds to observing an increase or decrease in the overall mean from 3.609 in group 1 to 4.175 in group 2. The sample size of 40 vaccinees per pooled group will give 80% power to detect a true difference of 0.80 standard deviations (SDs) between the mean non-zero responses and 90% power to detect a true difference of 0.90 SDs (these 2 are each conducted at a 5% alpha level). Using the mean and SD values from the HVTN 088 trial, the difference of 0.80 SDs translates to a difference of 0.313 units of  $\log_{10}$  binding magnitude; if 1 of the comparison groups has the same mean as was seen among non-negative values among vaccine recipients in the HVTN 088 trial (4.06 units), then after incorporating the expected 6% zero-valued (negative responder) measures, this corresponds to observing an increase or decrease in the overall mean from 3.722 in group 1 to 4.007 in group 2. These calculations assume a 10% loss-to-follow-up rate and the (94%) response rate observed in the HVTN 088 vaccine recipients. The same approach will be used to test superiority of the magnitude of the IgG binding Ab response to each individual gp120 antigen in the binding panel.

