### 6.4.4 Immunogenicity analysis

#### 6.4.4.1 General approach

Discrete categorical assay endpoints (eg, response rates) will be analyzed by tabulating the frequency of positive response for each assay by antigen and treatment arm at each timepoint for which an assessment is performed. Crude response rates will be presented with their corresponding 95% confidence interval estimates calculated using the score test method [59]. Because of the small numbers of control participants, no adjustment will be made to the vaccine arm estimates for the false positive rates in the control arms. To address the aims of Part B, Barnard or Fisher's exact tests, as specified in the SAP, will be used to compare the response rates of any 2 vaccine arms and of pooled groups as described in Section 4.1.2, with a significant difference declared if the 2-sided p-value is

$\leq 0.05$ . In general, Barnard's is preferred since under most circumstances it is more powerful than Fisher's [60].

In addition to response rate estimates for each timepoint, the probability of observing at least 1 positive response by a given timepoint and the probability of observing more than 1 positive response by a given timepoint will be estimated, with corresponding confidence intervals, for each vaccine arm using maximum likelihood-based methods [61].

For quantitative assay data (eg, magnitudes and magnitude-breadth AUCs from the neutralizing antibody multiplex assay or percentage of positive cells from the ICS assay), graphical and tabular summaries of the distributions by antigen, treatment arm, and timepoint will be made. For all primary and secondary immunogenicity endpoints, box plots and plots of estimated reverse cumulative distribution curves will be used for graphical display of all of the study arms. Typically the results will be shown for each vaccine arm and for the set of control arms pooled into 1 group.

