To test for differences among the vaccine arms in Part A and separately in Part B, first a Kruskal-Wallis rank test or an F-test (depending on the normality assumption) will be used to test for overall differences. Secondly, if the overall test is significant at the 2-sided 0.05 level, then individual tests comparing the 2 adjacent pairs of vaccine arms (Part A) and all 6 pairs of 4 vaccine arms (Part B) will be done unless pre-specified. If rank-based tests are used then the tests will be inverted to construct Hodges-Lehmann point estimates and 2-sided  $(1-0.05/k) \times 100\%$  CIs about the differences in location centers of the  $k = 2$  (Part A) or  $k = 6$  (Part B) pair-wise comparisons of vaccine arms. If actual-value tests are used then the Dunnett's procedure will be used to construct simultaneous confidence intervals about the pairs of mean differences for the many-to-one comparisons [62] when multiple vaccine arms are each compared with 1 common control arm. When all pair-wise comparisons between the multiple vaccine arms are of interest, the Tukey procedure [63] will be used. If only specific comparisons between pairs of the multiple vaccine arms are of interest, the Holm-Bonferroni procedure will be used. An appropriate data transformation (eg,  $\log_{10}$  transformation) may be applied to better satisfy assumptions of symmetry and homoscedasticity (constant variance). Significance of the differences between pairs will be evaluated using 2 procedures, first based on whether the simultaneous 95% CIs exclude zero and secondly based on whether the nominal (unadjusted) 95% CIs exclude zero.

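### Low severity: stratifying the two pooled Part B comparisons by the other randomized factor would protect their power at almost no cost, provided the two factors act roughly additively

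*Combined protocol and SAP*

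**What the plan says.** Section 6.1.2 sets two pooled Part B comparisons beside the six pairwise ones. The schedule comparison is made by "pooling over groups with and without mosaic DNA: Groups 5 and 6 combined vs Groups 7 and 8 combined". The DNA comparison sets Groups 5 and 7 against Groups 6 and 8. Each uses a two-sided Wilcoxon rank sum test at 5%, and no stratification is named. On power: "The sample size of 40 vaccinees per pooled group will give 80% power to detect a true difference of 0.80 standard deviations", with 90% at 0.90 SD. The spread comes from one vaccine arm of an earlier trial: "The standard deviation (SD) of the non-zero response was set to 0.391 for both groups".

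The background expects one of the factors to act. Section 4.1.3 says: "We hypothesize that the combined administration of DNA and protein will elicit stronger humoral and cellular responses than the protein alone". It gives no size. Section 4.5.1 is open about schedule. Giving each protein three times is something "which may be needed for optimal immune response to each immunogen to drive the desired B cell maturation", yet the same section also says: "If the sequential approach is as effective as the additive approach, the simplified immunization schedule would be preferable".

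Section 6.4.4.1 does not carry the pooled comparisons through for quantitative endpoints. After an overall test it lists the pairs only: "all 6 pairs of 4 vaccine arms (Part B) will be done unless pre-specified". Pooled groups appear there only for response rates, where exact tests "will be used to compare the response rates of any 2 vaccine arms and of pooled groups as described in Section 4.1.2". Section 4.1.2 is the study rationale; the pooled groups are defined in Section 6.1.2.

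**The concern.** When two regimens are merged into one side of a rank sum test, any difference between them becomes noise. The balance of the design keeps that difference out of the comparison itself, but an unstratified test still counts it as variability. The stated power therefore assumes that the merged factor does little, while Section 4.1.3 hypothesizes that DNA raises humoral responses.

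What is at stake is a missed difference in schedule or DNA effect, not a false positive. The trial already randomizes both factors, so analysing by them needs no new data.

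**Working it through.** **Inputs from Section 6.1.2.** Mean non-zero response 4.06 log10; SD 0.391; 6% zeros; 20 per group less 10% missing = 18 evaluable per group, 36 per pooled side; two-sided alpha 0.05.

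**Assumed.** The size of the merged factor's effect (0 to 1.63 SD), and additive effects on the log10 scale in the main table. The top value, 1.63 SD, is the plan's own pairwise detectable difference. It is an upper scenario, not an expected effect.

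**Method.** 100,000 simulated trials per setting. Rank sum: z = (W - E[W]) / sqrt(V), with tie-corrected V. Van Elteren: z = sum of w(W - E[W]) over the two strata, divided by sqrt(sum of w^2 V), with w = 1/(N + 1) and N the stratum size.

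**The plan's own figure.** With no effect of the merged factor, the unstratified test has 80.8% power at 0.80 SD (stated 80%) and 88.9% at 0.90 SD (stated 90%). The stated figures therefore include the zeros and the 10% loss, but no effect of the merged factor.

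**Power with an additive merged factor.** Fold change is 10^(effect x 0.391).

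| Merged factor | Fold | Unstratified, 0.80 SD | Van Elteren, 0.80 SD | Unstratified, 0.90 SD | Van Elteren, 0.90 SD |
|---|---|---|---|---|---|
| 0 | 1.0 | 80.8% | 80.4% | 88.9% | 88.4% |
| 0.4 SD | 1.4 | 79.7% | 80.4% | 87.8% | 88.1% |
| 0.6 SD | 1.7 | 78.4% | 80.6% | 86.7% | 88.3% |
| 0.8 SD | 2.1 | 75.7% | 80.3% | 85.0% | 88.4% |
| 1.2 SD | 2.9 | 69.2% | 80.4% | 79.7% | 88.3% |
| 1.63 SD | 4.3 | 59.3% | 80.3% | 71.2% | 88.6% |

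By symmetry, the same figures hold for the DNA comparison with schedule merged.

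**Hand check.** Merging two equal groups that differ by f SD multiplies the SD by sqrt(1 + f^2/4). At f = 0.8 this is sqrt(1.16) = 1.077, so 0.80 SD becomes 0.80/1.077 = 0.743 SD. Simulated power with no merged effect is 70.6% at 0.70 SD and 76.0% at 0.75 SD. Interpolation gives about 75%, in line with 75.7%.

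**Type I error.** Unstratified: 5.0%, 4.7%, 3.7%, 2.7% and 1.6% at merged effects of 0, 0.4, 0.8, 1.2 and 1.63 SD. Van Elteren: 4.9% to 5.0%. The planned test is conservative, not invalid.

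**Difference detectable with 80% power.** Unstratified: 0.310 log10 (merged effect 0), 0.328 (0.8 SD), 0.353 (1.2 SD). Van Elteren: about 0.311 throughout.

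**Without additivity.** The average schedule effect is held at 0.80 SD. DNA effect in the additive groups = DNA effect in the sequential groups + schedule effect with DNA - schedule effect without DNA.

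| Schedule effect without / with DNA (SD) | DNA effect, sequential / additive groups (SD) | Unstratified | Van Elteren |
|---|---|---|---|
| 1.0 / 0.6 | 0.8 / 0.4 | 77.8% | 79.7% |
| 1.2 / 0.4 | 0.8 / 0 (saturation) | 78.6% | 77.8% |
| 1.4 / 0.2 | 1.2 / 0 (saturation) | 74.9% | 74.0% |
| 1.6 / 0 | 1.6 / 0 (saturation) | 69.4% | 68.3% |
| 1.2 / 0.4 | 0.4 / -0.4 (reversal) | 79.6% | 77.5% |
| 1.6 / 0 | 0.8 / -0.8 (reversal) | 76.0% | 68.5% |
| 0.4 / 1.2 | 0.8 / 1.6 | 67.6% | 77.7% |

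The second and third saturation rows use 30,000 trials.

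**The case against.** The strongest reply is that nothing here is wrong. The stated power reproduces, false positives stay at or below 5%, and blocked randomization balances the groups, so this is a choice between two valid tests. That stands, and it is why the point is only an improvement.

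The gain is also modest next to other planning uncertainty. At a merged effect of 0.8 SD the detectable difference moves from 2.05-fold to 2.13-fold, while a planning SD that is 10% too low would by itself cut power to about 73%. The gain depends on rough additivity as well. It disappears under saturation and turns into a loss under reversal, and the documents do not say which pattern to expect. Both limits stand.

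Three stronger readings are tempting, and the documents do not support them.

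- A reader might infer that the power statement in Section 6.1.2 is wrong. It is right under its own assumption, and no document gives a DNA or schedule effect large enough to overturn it.
- A reader might infer that unequal missing data bias the comparison. With 16/20/20/16 evaluable in Groups 5/6/7/8 and a DNA effect of 0.8 SD, the contrast shifts by (20/36 - 16/36) x 0.8 = 0.089 SD. A shift that large in either direction has a chance of about 0.6% if 10% are missing at random. Under random missingness, power is 75.9%, the same as with balanced groups (75.7%). This pattern should carry no weight.
- A reader might infer that the primary neutralization result is at risk. The tier 1 and tier 2 screens against placebo in Section 6.4.4.2 do not pool across these factors. Section 6.1.2 does apply the pooled comparisons to neutralization, but gives no neutralization SD, so no loss can be computed.

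A separate SAP might name a stratified test. Section 6.1.2, however, already names the unstratified one.

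**Conclusion.** The point holds as a cheap, low-severity improvement. The planned pooled tests are valid but conservative. For binding antibody, a secondary endpoint in Part B, they lose about 1 point of power at a merged effect of 0.4 SD, about 5 at 0.8 SD and about 12 at 1.2 SD.

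These sizes assume a within-group SD of 0.391, a 94% response rate in every group, 18 evaluable per group and roughly additive effects. Separately, Section 6.4.4.1 omits the pooled comparisons of quantitative endpoints, so a sentence is needed there in any case.

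**What to change.** For the two pooled comparisons of participant-level quantitative endpoints, name a two-sided van Elteren test at 5%:

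- schedule, stratified by DNA: 5 vs 7 and 6 vs 8;
- DNA, stratified by schedule: 5 vs 6 and 7 vs 8.

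Report the stratified Hodges-Lehmann estimate with its 95% CI beside the two within-stratum estimates. Those four contrasts are already among the six pairs, and showing them would reveal an interaction, where a single common shift is harder to interpret. State this in Sections 6.1.2 and 6.4.4.1 and carry it into the SAP.

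Leave unchanged the six pairwise tests, the neutralization screens and any analysis of differential memory B cells that pools cells across participants, which a participant-level test does not fit.

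The cost is one sentence in each place, with no added participants or data. In power, it is about half a point if the merged factor is inert (80.8% to 80.4% at 0.80 SD), about 1 point under saturation, and up to about 7 points (76.0% to 68.5%) in the most extreme reversal examined.

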## 6.2 Randomization

The randomization sequence will be obtained by computer-generated random numbers and provided to each HVTN CRS through a Web-based randomization system. The randomization will be done in blocks to ensure balance across arms. At each institution, the pharmacist with primary responsibility for dispensing study products is charged with maintaining security of the treatment assignments (except in emergency situations as specified in the HVTN MOP).

## 6.3 Blinding

Participants and site staff (except for site pharmacists) will be blinded as to participant treatment arm/group assignments (eg, vaccine or control). Study product assignments are accessible to those HVTN CRS pharmacists, DAIDS protocol pharmacists and contract monitors, and SDMC staff who are required to know this information in order to ensure proper trial conduct. Any discussion of study product assignment between pharmacy staff and any other HVTN CRS staff is prohibited. The HVTN SMB members also are unblinded to treatment assignment in order to conduct review of trial safety.

When a participant leaves the trial prior to study completion, the participant will be told he or she must wait until all participants are unblinded to learn his or her treatment assignment.

Emergency unblinding decisions will be made by the site investigator. If time permits, the HVTN 115 PSRT should be consulted before emergency unblinding occurs.

## 6.4 Statistical analyses

This section describes the final study analyses, unblinded as to treatment arm/group assignment. All data from enrolled participants will be analyzed according to the initial randomization assignment regardless of how many vaccinations they received. In the rare instance that a participant receives the wrong treatment at a specific vaccination time, the Statistical Analysis Plan (SAP) will address how to analyze the participant's safety data. Analyses are modified intent-to-treat in that individuals who are randomized but not enrolled do not contribute data and hence are excluded. Because of blinding and the brief length of time between randomization and enrollment—typically no more than 4 working days—very few such individuals are expected.

Analyses for primary endpoints will be performed using SAS and R. All other descriptive and inferential statistical analyses will be performed using SAS, StatXact, or R statistical software.

No formal multiple comparison adjustments will be employed for multiple safety endpoints, multiple primary immunogenicity endpoints, or secondary endpoints. However, multiplicity adjustments will be made for certain immunogenicity assays, as discussed below, when the assay endpoint is viewed as a collection of hypotheses (eg, testing multiple peptide pools to determine a positive response).

